	Pre-intervention	Post-intervention	Follow-up interview/recording (intervention arm only)
Demographics	X		
Provider burnout	X	X	
Provider/patient engagement in shared decision-making, measured qualitatively	X		X

B. Sample Size:

Specific Aim 1: We based our sample size calculation on our primary outcome, contraceptive continuation. Based on our previous studies in this population, we estimate that 50% of women in our control group will continue with their contraceptive method at seven months. Using this same data, we have calculated the intra-cluster correlation (ICC) of this response by provider and by clinic at ~0 and 0.021 respectively. Accounting for clustering and 20% loss to follow-up, as well as a inflation factor to account for differences in contraceptive initiation among those in clinics with IUDs and implants on-site as compared to those without these methods on site, a sample of 758 patients (approximately 32 patients for each of 24 providers) would provide 80% power in 2-sided tests with a type-I error rate of 5% to detect a 12 percentage point increase in continuation, to 62%. This difference in contraceptive continuation would be clinically meaningful and is consistent with effects reported in the contraceptive literature. Again using data from our previous study to estimate ICCs and baseline parameters, the sample will also provide 80% power to detect small-to-moderate but clinically significant differences in secondary outcomes as shown below.

Study Protocol

Patient Centered Support for Contraceptive Decision-Making: A Cluster Randomized Controlled Trial of a Contraceptive Decision-Support Tool

November 22, 2016

Outcome	ICC		Design effect	Baseline SD/%	SES/ MDD
	Clinic	Provider			
Continuous measures					
Decision conflict scale	0.000	0.027	1.3	1.9	0.25
Satisfaction score	0.152	0.075	1.7	6.5	0.31
Dichotomous measures					
Choice of highly effective method	0.096	0.000	0.9	23%	10.9%
Shared decision making	0.006	0.024	1.3	46%	14.3%
Unintended pregnancy	0.005	0.001	1.0	5%	-4.5%
For continuous outcomes, the standard deviation (SD) and standardized effect size (SES) are reported; for binary outcomes, the baseline prevalence and absolute effect, both in percent.					

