Analysis Plan: Patient Centered Support for Contraceptive Decision-Making: A Cluster Randomized Controlled Trial of a Contraceptive Decision-Support Tool

Principal Investigator: [name] MAS

Intention-to-treat analysis

Participants who “cross over” from their assigned study arm (as determined by the provider they are likely to see) will be included in the final analyses in the arm in which they were initially assigned.

Modified intention-to-treat analysis: Post-randomization exclusion

Some participants may be excluded from analysis after being randomized:

- Participants who find out they are pregnant during their enrollment visit (and thus would have been ineligible had this been known prior to enrollment).
- Participants who enrolled in the study more than once (their second enrollment will be excluded).

Data Collection and Analysis

The outcomes of interest for this study have been divided into three specific aims, which dictate what type of data is collected and how it is analyzed.

Outcomes of Interest

Specific Aim 1: The primary outcome is a binary indicator of contraceptive continuation at 7 months and a secondary outcome is a binary indicator of contraceptive continuation at 4 months. For ambiguous cases for these outcomes, we used a blinded adjudication process and applied a standardized list of rules and assigned outcomes throughout the process of data collection. Potential outcomes for individuals are as follows: continuous users of chosen method, non-continuous users of chosen method, and missing but included and imputed.

For all variables, the analysis will use multiple imputation to deal validly with the missing values. Of note, specific variables were not collected from participants we collected data from more than 48 hours after their visit. Those variables will be analyzed in the same way as other missing outcomes.

- **Primary outcome:**

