We will assess imbalance by treatment assignment using cross-tabulations and comparisons of within group means and medians. Inference for balance on provider covariates will use chi-squared, Fisher's exact, t, and Wilcoxon tests as appropriate, while differences in patient characteristics will be assessed using mixed effects models with fixed effects for clinic and random effects for provider. [IR-3] Primary analyses of treatment effects will be intention-to-treat, according to treatment assignment, and without regard to use of the tool or seeing an intervention provider. Treatment effects will be estimated using mixed effects linear, logistic, proportional odds, and multinomial models, with fixed effects for clinic and random effects for provider.

Missing data. [MD-1] Missing data will have been minimized by active follow-up of participants. [MD-4] Missing data rates for primary and secondary outcomes as well as important covariates will be reported, in combination with summaries of the reasons for missingness, including dropout and pregnancy. [MD-2] All analyses will handle missing data using 20-fold multiple imputation of missing outcomes, based on iterative chained equations. [MD-3] Summary effect estimates, averaged over the 20 imputed datasets, as well as confidence intervals and p-values, will be calculated using standard methods that account for imputation error.

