Sensitivity analyses. [MD-5] Because informative missingness would violate the covariate-dependent missing at random (CDMAR) assumption of the standard multiple imputation procedure, we will conduct sensitivity analyses in which we multiply impute missing data under plausible informative missing data mechanisms – in particular, lower contraceptive continuation rates among participants with missing values of this outcome, in one or both arms. [DR-3] In addition, we will conduct sensitivity analyses controlling for any imbalanced pre-randomization characteristics (e.g., age and parity) that predict outcomes, using 5% changes in the coefficient for the intervention as the criterion for covariate inclusion in the adjusted model. To characterize the influence of individual providers, we will estimate best linear unbiased predictions of the provider effects, and also fit models with additional random provider-intervention interactions, to capture heterogeneity in the effects of the intervention. In all analyses, we will transform continuous outcomes as necessary to meet the normality assumption, model departures from linearity in the influence of continuous covariates, check for influential points, and identify potentially important interactions.

Heterogeneity of treatment effects. [HT-1] We will assess modification of the effect of assignment to the intervention by the following 5 pre-specified factors: age, race/ethnicity, language, parental education, and clinic. We will assess evidence for effect modification by adding the effect modifier and its interaction with the treatment assignment indicator to the primary analysis models specified above. To limit inflation of the type-I error rate, we will only estimate within-stratum treatment effects if the interaction is statistically significant at a Bonferroni-corrected $P = 0.01$, and will cautiously interpret findings. These analyses will use multiply imputed data and corresponding inference methods.

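### The imputation plan leaves out provider and arm-by-modifier terms; run as ordinary chained equations, it would understate some secondary-outcome standard errors and shrink the interaction estimates

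*SAP*

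**What the plan says.** Both documents give the same missing-data rule under Methods of Analysis, Specific Aim 1: "All analyses will handle missing data using 20-fold multiple imputation of missing outcomes, based on iterative chained equations". Pooled intervals and p-values "will be calculated using standard methods that account for imputation error". The sensitivity-analysis paragraph refers to the "covariate-dependent missing at random (CDMAR) assumption of the standard multiple imputation procedure". No list of imputation predictors follows. Provider, clinic, arm and arm-by-modifier terms are not mentioned in connection with the imputation.

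The analysis depends on provider throughout. Providers are randomised within clinic (Protocol III.A.2). Treatment effects come from "mixed effects linear, logistic, proportional odds, and multinomial models, with fixed effects for clinic and random effects for provider". Further analyses predict individual provider effects and "fit models with additional random provider-intervention interactions, to capture heterogeneity in the effects of the intervention".

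Two other places send imputed data into the results. SAP, Outcomes of Interest, Specific Aim 1, notes that "specific variables were not collected from participants we collected data from more than 48 hours after their visit" and treats those values like other missing outcomes. The heterogeneity paragraph tests five modifiers (age, race/ethnicity, language, parental education, clinic) and adds that "These analyses will use multiply imputed data and corresponding inference methods".

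**The concern.** An imputation model should contain the structure that the analysis model relies on. Here the precision of the arm comparison rests on variation between providers. A value imputed from arm and covariates alone has no provider component. It pulls each provider's mean toward the mean of its arm and clinic, so the completed data show less between-provider variance than the real data would. Confidence intervals for outcomes with provider clustering then come out too narrow.

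The same logic applies to effect modification. If arm-by-modifier terms are absent from the imputation, imputed women carry no interaction and dilute the estimate toward zero.

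At stake are the patient-experience outcomes of Aim 1, the provider-heterogeneity analyses and the five interaction tests. The main effect on continuation is not at stake.

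**Working it through.** The plan prints no figure for the effect of imputation, so there is none to reproduce. The check asks what would happen if provider were left out.

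**Inputs from the documents**
- "a sample of 758 patients (approximately 32 patients for each of 24 providers"; 758/24 = 31.6, taken as m = 32. Four clinics, 12 providers per arm (Protocol VII.B).
- Provider ICC (Protocol VII.B): continuation about 0, decisional conflict 0.027, shared decision making 0.024, satisfaction score 0.075.
- M = 20 imputations.

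**Assumptions.** Missing fraction f = 5%, 10% or 20% (the documents give no post-visit rate); data missing at random; continuous outcomes; equal provider sizes; only arm and clinic in the single-level imputation.

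**Formula.** Take total variance within arm and clinic as 1, and write ρ for the provider ICC. Per provider:
- True variance of the contribution to the arm mean: ρ + (1−ρ)/(m(1−f)).
- Variance reported after single-level imputation: (1−f)²ρ + [1−(1−f)ρ]/m + (1+1/M)·f/(m(1−f)).

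The first reported term shows the problem: between-provider variance is multiplied by (1−f)². At f = 0.20, 0.075 becomes 0.64 × 0.075 = 0.048.

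**Example, ρ = 0.075, f = 0.20**
- True: 0.075 + 0.925/25.6 = 0.1111.
- Reported: 0.048 + 0.94/32 + 1.05 × 0.20/25.6 = 0.048 + 0.0294 + 0.0082 = 0.0856.
- SE ratio: √(0.0856/0.1111) = 0.878, so the SE is about 12% too small.

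**Reported SE divided by true SE, by formula**

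| Missing | ρ = 0.027 | ρ = 0.075 |
|---|---|---|
| 5% | 0.979 | 0.966 |
| 10% | 0.960 | 0.934 |
| 20% | 0.929 | 0.878 |

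At ρ = 0.024 and 20% missing the ratio is 0.934. If the satisfaction ICC is re-expressed within clinic, 0.075/(1−0.152) = 0.088, it is 0.870.

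**Simulation under the null** (fixed clinic, random provider, Rubin pooling; 4,000 replicates per cell; error about 1% on ratios and 0.3–0.4 points on rejection)
- 20% missing: SE ratio 0.945 (ρ = 0.027) and 0.879 (ρ = 0.075). With small-sample degrees of freedom for the pooled test, type I error is 4.9% and 7.0%.
- 10% missing: 0.953 and 0.952; type I error 4.9% and 6.1%.
- 5% missing: 0.991 and 0.963; type I error 4.6% and 5.3%.

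A separate simulation of 2,000 replicates gave 0.928 and 0.865 at 20% missing. With a random provider effect in the imputation, the ratio returned to 0.98–1.03 in every cell with ρ from 0.024 to 0.075. At ρ = 0 single-level imputation gave no understatement (1.04–1.07). With a normal reference in place of t, rejection at ρ = 0.075 and 20% missing was 10.0%. It was already 7.3% with complete data, so much of that excess comes from having 24 clusters and not from imputation.

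**Provider indicators instead of a random effect.** At ρ = 0.027 and 20% missing the SE is about 9–12% too large, and rejection falls to about 2.5%.

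**Interactions.** If imputed women carry zero interaction, the pooled estimate is about (1−f)β + f·0. At f = 0.20 that is 0.80β. A simulation with true log odds ratio 0.8 and N = 6,000 gave 0.63 with the term omitted, against 0.79; 0.63/0.79 = 0.80. The large N serves only to measure the bias and says nothing about power in this trial.

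**The case against.** The strongest reply is that the documents do not say provider is left out. The imputation sentence gives the number of imputations and the algorithm. The word standard is set against imputation under informative missingness, not against multilevel imputation. This stands: a reader might infer that the plan excludes provider and that its standard errors are therefore wrong, but the text supports only a conditional statement. Single-level imputation is still the natural reading of ordinary chained equations when no cluster term is named.

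The second reply concerns the missing rate, and it also stands. The clustered outcomes come from the post-visit survey, which is completed at the clinic or soon after by phone or email (Protocol III.B), and the first gift card is tied to completing it (Protocol VI). Only time-sensitive questions are omitted after 48 hours, and neither document says that satisfaction, decisional conflict or shared decision making are among them. The 20% in the sample size section is loss to follow-up for continuation. Reading it as the post-visit rate is not supported. At 5% missing, rejection cannot be distinguished from the nominal 5%.

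Third, the largest ICC belongs to the continuous satisfaction score, whereas the SAP analyses the top score against all others, and shared decision making is split into several items. The ICCs of the analysed variables may differ.

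Finally, the interaction tests are gated at P = 0.01 and are to be read cautiously. That guards against false positives. It does nothing against shrinkage toward zero.

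**Conclusion.** The point holds in conditional form. The plan does not bring provider or arm-by-modifier terms into the imputation. Run as ordinary single-level chained equations, it would make standard errors for outcomes with provider ICC of 0.024–0.075 at most about 3% too small at 5% missing, 3–7% at 10% and 7–12% at 20%, with type I error about 7% at worst. This assumes 24 providers of about 32 women, data missing at random and the printed ICCs. Other imputation predictors that themselves vary by provider would reduce the loss.

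It would be wrong to conclude that the primary result is unsafe: provider ICC for continuation is near 0, and its main effect is essentially unaffected. The primary outcome is touched only through its interaction tests, which would shrink by roughly the missing fraction, or about 20% at the planned loss. The actual fraction may differ, because women already discontinuous at 4 months are counted as negative at 7 months without imputation, while some pregnancies are added to the imputed group.

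This should be fixed, but it does not threaten the trial's main conclusion.

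**What to change.** In the missing-data paragraph of both documents, under Methods of Analysis, Specific Aim 1:
- Specify multilevel imputation with a random intercept for provider, and include clinic and arm.
- List the remaining predictors, including the five effect modifiers.
- Impute separately by arm, or include arm-by-modifier terms for all five modifiers, before the heterogeneity tests. Imputing by arm works only if the modifiers are themselves predictors.
- Do not make provider indicators the default, because they overcorrect when the ICC is small.
- Report the missing rate for each post-visit outcome and name the items omitted after 48 hours, so that readers can judge how much the imputation matters.

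The cost is a few sentences and some extra programming, mainly for random-intercept imputation of binary and ordinal outcomes. No new data are needed.

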This is a cluster randomized controlled trial to investigate the effect of our contraceptive decision support tool on women's contraceptive continuation, as well as on their experience of contraceptive counseling, measured both quantitatively and qualitatively. In addition, we will collect quantitative and qualitative data to determine the impact of the implementation of this tool on the experience of providers and the clinics in which they work. Data collection will occur in three stages: 1) pre-intervention phase, 2) intervention phase, including follow-up of patients for seven months, and 3) post-intervention phase. For phase 1, immediately before implementing the contraceptive decision support tool, we will collect audio recordings of contraceptive counseling visits. For phase 2, we will randomize at the provider level to usual care or use of the intervention. For phase 3, we will conduct audio recordings of contraceptive counseling visits with providers in the intervention arm, as well as performing interviews of intervention providers and focus groups with clinic staff. We will use best practices for the conduct and reporting of this type of trial as detailed in the CONSORT guidelines.

III. Study Procedures

As described, this study has three main phases, outlined below. All study procedures will be conducted by UCSF study staff or UCSF study volunteers.

A. Pre-Intervention Phase Procedures

In the pre-intervention visit recording phase, we will recruit patients at the study clinics prior to implementing the intervention. Subsequently, providers will be randomized into the control or intervention arm of the study.

1. Pre-Intervention Audio Recordings

The procedure for provider participants is as follows:

- The study will be discussed at staff meetings or individually, as determined by each clinic.
- Each potential participant will then be contacted individually to have their questions answered and determine if they are willing to consent to participate. Study staff will obtain written consent for the pre-study visit recording phase and the study intervention phase at this time.
- After enrolling in the study, each provider will conduct 2-3 family planning visits in the usual fashion as are performed at the clinic with patients participating in this phase of the study.
- During these visits, the conversation between patient and provider will be recorded on a secure voice recorder.

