- The recordings from these visits will be transcribed on a computer by a HIPAA-compliant transcription service.

Study Protocol

Patient Centered Support for Contraceptive Decision-Making: A Cluster Randomized Controlled Trial of a Contraceptive Decision-Support Tool

November 22, 2016

- After completing three visits, each provider will complete a survey about their demographic characteristics and the Maslach Burnout Inventory.

The procedure for patient participants is as follows:

- After being screened and consented by study staff, each patient will complete a short demographic survey (**Note:** This survey was not added to study procedures until 11/4/15, when a minor modification detailing it was approved) and have a family planning visit in the usual fashion as is performed at the clinic with providers participating in the study. As described above, the conversation between patient and provider will be recorded on a secure voice recorder during these visits, and the visits will be transcribed.

2. Randomization

After the pre-intervention phase and before the intervention phase, the provider participants will be randomized into intervention and control arms, stratified by clinic. Providers will be randomized using a random number table, clustered by each clinic. [name] will create a random number table using Stata 13's "ralloc" randomization module and blinded study IDs provided by study staff. The decision support tool intervention will then be introduced in a short orientation to the providers randomized to the intervention arm.

B. Intervention Phase Procedures

Study staff role: UCSF Research Assistants will track all recruitment activity using the clinic-specific Recruitment Tracking Log daily. Weekly totals will be tallied each Friday afternoon. At each recruitment shift in each clinic, there should be one UCSF Research Assistant (RA) who conducts eligibility and consent processes, and, if possible, one volunteer or Patient Stakeholder Representative who assists the RA with completing tracking logs, the time study, and managing iPads and other study equipment. Time study data will be collected in this phase the same as in the pre-intervention phase: patient arrival time, tool start and end time (if applicable), visit start time with clinician, and visit end time.

The procedure for provider participants is as follows:

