- **Some patient participants may be randomized** to whether they see a control or intervention arm provider, if they are at a clinic that does not make appointments with specific providers and there are providers in both arms that are available to have an appointment with that provider. Both City Clinic and Planned Parenthood Valencia do not assign patients to a specific provider in advance of the start of their visit. Therefore, at these clinics, sometimes it will not be clear whether or not a participant should use the tool or not before her visit. At these two clinics, the RA who is recruiting will first see if it is obvious which study arm the patient should be in based on which providers are currently available to see family planning patients. In some cases, only one study provider will be working at a time, or all the study providers who are working will be in the same arm, so it will be clear which arm the patient should be in. At other times, multiple providers may be working but there may be only one who speaks the patient's language or who is not about to start a long procedure, so it is clear which arm the patient will be in. In the remainder of cases, in which there is at least one provider from each study arm (tool and control) available to see patients at the same time, the RA will use a program written in R, the statistical software program, to randomly assign the patient to see either a tool or control provider. The randomization module was written by [name], our study statistician, and is installed on the study laptops and RA iPhones. An RA simply has to open R and type in the command "randomize" along with the ratio of tool to control arm providers who are currently available (i.e., "Randomize(1,1)") and the program will produce an assignment. The RA will then do her best to work with clinic flow to ensure that the patient sees a provider in the appropriate arm. As described in the analysis section, if the patient ultimately sees a provider in the non-randomized arm, she will be analyzed in the assigned arm using intention to treat principles.

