Specific Aim 2: We have estimated that audio recording 2-3 patient encounters at each time point (before and after implementation of the intervention) for each of the providers randomized to the intervention will allow us to achieve saturation and to meaningfully compare the pre- and post-intervention period.

Specific Aim 3: We will conduct focus groups at each of the four clinics involved in the study, and will conduct semi-structured interviews of each of the providers randomized to the intervention. For our quantitative measures, we estimate we will have the ability to detect a less than 0.5 SD difference in consultation time and total clinic visit time. For comparison of burnout among providers, our sample size will be 24, with 12 in each group, and therefore will have limited power. In order to optimize power, we will estimate treatment effects on the final score controlling for the baseline value. Using this measure, we anticipate having 80% power to detect a 0.5 to 1.1SD differences on each of the sub-scales of the Maslach Burnout Inventory, depending on with within-provider correlation of these responses.

C. Methods of Analysis

Patient and provider stakeholders will be involved in an iterative manner in all stages of planning of analyses and in data interpretation.

[IR-1] Data required for primary analyses will be inspected, cleaned, and locked before primary analysis is begun. Data checks will include examination of descriptive statistics for plausibility (e.g. plausible

Study Protocol

Patient Centered Support for Contraceptive Decision-Making: A Cluster Randomized Controlled Trial of a Contraceptive Decision-Support Tool

November 22, 2016

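### The random provider-by-intervention term estimates only the excess between-provider variance in the tool arm, so a zero estimate does not show that the effect is uniform across providers

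*SAP*

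**What the plan says.** Protocol II states that "we will randomize at the provider level to usual care or use of the intervention", and Protocol III.A.2 that "the provider participants will be randomized into intervention and control arms, stratified by clinic". For the burnout comparison, Protocol VII.B says "our sample size will be 24, with 12 in each group".

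The Aim 1 models are mixed models "with fixed effects for clinic and random effects for provider". To these, the sensitivity-analysis paragraph (the same text in SAP and Protocol VII.C) adds best linear unbiased predictions of the provider effects and a plan to "fit models with additional random provider-intervention interactions, to capture heterogeneity in the effects of the intervention". It gives no covariance structure for the two random terms, no independence assumption, and no rule for reading the result.

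Before randomization, Protocol II says that "immediately before implementing the contraceptive decision support tool, we will collect audio recordings of contraceptive counseling visits". Protocol III adds a short patient demographic survey, a provider survey and visit times for that phase. None of these is an Aim 1 outcome such as continuation, satisfaction, decisional conflict or patient-reported shared decision making.

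**The concern.** Heterogeneity of effect across providers means that the difference between a provider's results with and without the tool varies from provider to provider. In this design that difference is not observed for any provider on the Aim 1 outcomes. What can be compared is the spread of provider results in one group of providers with the spread in another.

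The two are linked, but they are not the same quantity. Suppose that providers whose patients fare worse under usual care gain more from the tool. Effects then vary, yet the spread in the tool arm may be no larger than in the control arm, or may be smaller. The planned term would be near zero in either case. At stake is how a secondary finding is read: a zero could be taken as reassurance that the tool works alike for all providers, and a non-zero value could be taken as the size of the variation.

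**Working it through.** The documents give no figure for this analysis, so there is none to reproduce. The sample size enters only to set the number of patients per provider.

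**Inputs**
- 24 providers, 12 per arm, each in one arm (Protocol II, III.A.2, VII.B).
- "a sample of 758 patients (approximately 32 patients for each of 24 providers) would provide 80% power in 2-sided tests". With the planned 20% loss, 758 × 0.8 / 24 ≈ 25 analysed patients per provider.
- Provider ICCs from the Protocol VII.B text and table: continuation ~0, shared decision making 0.024, decisional conflict 0.027, satisfaction 0.075.
- Assumptions: the interaction is a random slope on a 0/1 arm indicator, and total outcome variance is scaled to 1, so that SDs are in outcome-SD units.

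**Step 1. What is identified.** Let u be a provider's level under usual care and v that provider's own effect.
- Control arm: t0² = Var(u)
- Tool arm: t1² = Var(u) + Var(v) + 2Cov(u,v)

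There are two estimable variances and three unknowns. With u and v modelled as independent, the fitted interaction variance targets t1² − t0² = Var(v) + 2Cov(u,v), cut off at 0. It equals Var(v) only if Cov(u,v) = 0.

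**Step 2. The likelihood cannot separate the cases.** Take Var(u) = 0.075 with
- Var(v) = 0.075, Cov = 0: tool-arm variance 0.075 + 0.075 = 0.15
- Var(v) = 0.225, Cov = −0.075: 0.075 + 0.225 − 0.150 = 0.15
- Var(v) = 0.0336, Cov = 0.0207: 0.075 + 0.0336 + 0.0414 = 0.15

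On one dataset all three give the same REML objective, 201.6285, although Var(v) differs 6.7-fold (0.225 / 0.0336).

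**Step 3. Bounds.** Let r be the correlation between a provider's level with the tool (u + v) and without it (u). Then Var(v) = t0² + t1² − 2r·t0·t1, and r between −1 and 1 gives |t1 − t0| ≤ SD(v) ≤ t1 + t0.

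| Case | t0 | t1 | SD from planned term | Bounds on SD(v) |
|---|---|---|---|---|
| Shared decision making, equal variances | 0.155 | 0.155 | 0 | 0 to 0.31 |
| Decisional conflict, equal variances | 0.164 | 0.164 | 0 | 0 to 0.33 |
| Satisfaction, equal variances | 0.274 | 0.274 | 0 | 0 to 0.55 |
| Satisfaction, tool-arm variance doubled | 0.274 | 0.387 | 0.27 | 0.11 to 0.66 |

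The top of each range needs r = −1, a full reversal of provider ranking. If r is assumed to be at least 0, the satisfaction limit with equal variances is √(2 × 0.075) = 0.39. That still exceeds the 0.31 SD treatment effect which Protocol VII.B gives as detectable for this score.

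**Step 4. Narrowing.** With Var(u) = 0.075, Var(v) = 0.05 and Cov = −0.05, the tool-arm variance is 0.075 + 0.05 − 0.10 = 0.025. The excess is −0.05 and the constrained target is 0, although SD(v) = √0.05 = 0.22.

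**Step 5. Simulation** (linear mixed model, 400 runs per case, 4 clinics with 3 providers per arm each, 25 patients per provider, Var(u) = 0.075, residual variance 0.75 assumed)

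| True Var(v) | Tool-arm variance | Mean fitted interaction variance | Test rejects |
|---|---|---|---|
| 0 | 0.075 | 0.028 | 5% |
| 0.075 | 0.075 | 0.028 | 4% |
| 0.15 | 0.075 | 0.028 | 4% |
| 0.05 | 0.025 | 0.006 | 1% |
| 0.0336, 0.075 or 0.225 | 0.15 | 0.084 to 0.091 | 18 to 21% |

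The fitted value follows the tool-arm variance, not Var(v). The mean of 0.028 in the first row is sampling error cut off at zero (median 0.000). With Var(u) set to about 0 and Var(v) = 0.075, the mean was 0.068, so in that case the term does approximate heterogeneity.

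**The case against.** The strongest reply is that the term is estimable and informative. Providers are randomized within clinic, so Var(u) has the same expectation in both arms, and on the model's scale an identical effect for every provider leaves the provider variance unchanged. A true variance difference in either direction therefore does imply heterogeneity, with an SD of at least |t1 − t0|. This stands. A reader might infer that the term can never detect heterogeneity, or that a positive value might reflect only more variable providers in one arm. The design does not support either reading, beyond chance imbalance between about 12 providers per arm.

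Second, Protocol VII.B gives a provider ICC of ~0 for continuation. If Var(u) is about 0, so is Cov(u,v), and the excess variance approximates Var(v). This stands too, as far as that planning value is right.

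Third, neither document says that a zero will be reported as a uniform effect. The analysis is described as characterizing individual providers' influence, and the formal subgroup work is the separate heterogeneity paragraph. That is fair: the weakness is an unstated assumption behind the stated purpose, not a wrong conclusion already written into the plan.

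Fourth, patients at City Clinic and Planned Parenthood Valencia may cross over: "if the patient ultimately sees a provider in the non-randomized arm, she will be analyzed in the assigned arm using intention to treat principles". If the random effect indexes the provider seen, a few providers could have patients from both assignments. The plan does not say which provider is indexed or how many crossovers it expects. Such patients were not randomized to that provider and say little about the provider's own effect.

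Finally, arm-specific variances are nearly the same model in another form. They differ in one respect that matters: they can show a smaller spread in the tool arm.

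**Conclusion.** The point holds, as a minor one. The planned term measures the excess between-provider variance in the tool arm. It can indicate heterogeneity, but it cannot rule it out, cannot size it without a zero-covariance assumption that the plan does not state and the data cannot test, and cannot register a narrowing of provider differences.

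It matters mainly for secondary outcomes with a provider ICC above 0 (0.024 to 0.075 for shared decision making, decisional conflict and satisfaction). With equal arm variances the target is 0, while the SD of provider effects may be as large as 0.31 to 0.55 outcome SDs. These figures rest on the planning ICCs and a linear scale. The SAP top-scores satisfaction and analyses the shared decision making items as categories, so for those outcomes the same algebra applies on the model's own scale with different numbers.

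A reader might infer that the trial's main result is in doubt. It is not: this is a sensitivity analysis, and the primary treatment-effect test does not depend on it.

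**What to change.** In the sensitivity-analysis paragraph of the SAP and of Protocol VII.C:

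1. Replace the random provider-by-intervention interaction with separate between-provider variances for each arm, free to be larger or smaller in the tool arm.
2. Report the provider SDs t0 and t1 with intervals, and the bounds |t1 − t0| to t1 + t0 on the SD of provider-specific effects. If a single value is given instead, state that it assumes zero covariance between usual-care level and effect.
3. State that equal variances are not evidence of a uniform effect.
4. Keep the planned clinic-by-intervention interaction as a separate question. It is estimable because randomization is stratified by clinic, but it concerns variation across four clinics and does not replace the provider-level question.

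The cost is one changed model line and a few sentences in two documents, with no new data. Precision will be poor whichever form is used: with about 12 providers per arm, even a doubled tool-arm variance was detected in only about 20% of simulated trials.
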